2.2. Study Objective(s) and Endpoint(s)

Group 1 – Women in Third Stage of Labour (TSL)

Objectives	Endpoints
Primary Objectives	Primary Endpoints

 To characterize the pharmacokinetics of single doses of IH oxytocin and 10 International Units (I.U.) IM oxytocin in women in TSL. 	
 Plasma concentration time profile for IH oxytocin and 10 I.U. IM oxytocin. PK parameters: Maximum observed plasma concentration (C_{max}), Observed plasma concentrations at 10 minutes (min) postdose (C_{p10}), Observed plasma concentrations at 20 min post-dose (C_{p20}), Observed plasma concentrations at 30 min post-dose (C_{p30}), Time to C_{max} (t_{max}), Area under concentration-time curve (AUC), and Terminal phase half-life (t_{1/2}) will be calculated as data permit.
Secondary Objectives	Secondary Endpoints

 To evaluate the safety and tolerability of inhaled oxytocin. To compare pharmacokinetics of IH oxytocin to 10 I.U. IM oxytocin in women in TSL. 	
 General safety parameters: adverse events (AE); absolute values and changes over time of vital signs (blood pressure, heart rate, respiratory rate, temperature). C_{max}, C_{p10}, C_{p20}, C_{p30}, Area under the concentration-time curve from time zero (pre-dose) to three hours (h) (AUC[0-3h]) will be compared as data permit.
Exploratory Objectives	Exploratory Endpoints

 Pharmacodynamic effect of IH oxytocin and 10 I.U. IM oxytocin in women in TSL. Participant feedback regarding ease of use, instructions, and perceived ability of patients to use the ROTAHALER. 	
 Pre and post-delivery haemoglobin Questionnaire results from participants.

Group 2 – Non-pregnant, non-lactating females of child bearing potential

Objectives	Endpoints
Primary Objectives	Primary Endpoints

 To evaluate the safety and tolerability of IH and IV Oxytocin 	
 General safety parameters: adverse events; absolute values and changes over time of vital signs (blood pressure, heart rate) and 12-lead electrocardiogram (ECG) parameters (PR, QRS, QT, Corrected QT interval [QTc] intervals) from pre-dose values. Specific respiratory safety parameters: adverse respiratory events as monitored by spirometry including Forced expiratory volume at 1 minute (FEV_{1.0}), respiratory rate, and pulse oximetry.

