4. ANALYSIS POPULATIONS

Population	Definition / Criteria	Analyses Evaluated
Screened	
 All participants who were screened for eligibility 	
 Screen Failures
Enrolled	
 All participants who passed screening and entered the study including randomized participants and run in failures 
Note: Screening failures (who never passed screening even if rescreened) and participants screened but never enrolled into the study (Reserve, Not Used) are excluded from the Enrolled population as they did not enter the study.
	
 Study Population
Safety	
 Comprise of subjects who receive at least one dose of study medication. This population will be used for the study population and safety displays. 
Note: This population will be based on the treatment the participants actually received
	
 Study Population Safety
Pharmacokinetic (PK)	
 Subjects in the 'Safety' population for whom a pharmacokinetic sample was obtained and analysed. PK population will be the population for reporting PK data. 	
 PK

Refer to [Appendix 12](#): List of Data Displays which details the population used for each display.

CONFIDENTIAL

205920

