4.1. Protocol Deviations

Protocol deviations will be tracked by the study team throughout the conduct of the study in accordance with the Protocol Deviation Management Plan.

- Data will be reviewed prior to freezing the database to ensure all important deviations are captured and categorised on the protocol deviations dataset.
- The SI dataset will include all protocol deviations; the analysis dataset will include only important protocol deviations. The analysis dataset will be used for the listing of important protocol deviations.
- The study endpoints will be reported using the populations detailed in Section 4 of this document regardless of whether the participants deviate from the protocol.
- A separate listing of all inclusion/exclusion criteria deviations will also be provided. This listing will be based on data as recorded on the inclusion/exclusion page of the eCRF.

CONFIDENTIAL

205920

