Descriptive Summary Statistics. (Loge Transformed)	N, n, geometric mean, 90% CI of geometric mean, standard deviation (SD) of logged data and between geometric coefficient of variation (CVb (%)) will be reported. $CVb (\%) = \sqrt{(\exp(SD^2) - 1) * 100}$ [NOTE: SD = SD of loge transformed data] Following steps can be used to calculate 90% CI for PK parameters: Standard Error = [(Geometric Stdev-1)/Sqrt(N)], Margin of Error = [Standard Error * 1.645], and CI = [Geometric Mean \pm Margin of Error]	
Parameters Not Being Loge Transformed	Tmax, and t1/2	
Summary Tables	The following PK parameters will not be summarised: tlast, Lambda_z, Lambda_z_lower, Lambda_z_upper, #pts and r-squared . The following PK parameters will not be log-transformed: Tmax, t1/2 All other parameters will be summarised as log-transformed and non-log-transformed data as described in Section 8.1.2.	
Listings	Include PK Parameters Cmax, Clast, tmax, tlast, AUC(0-3h), AUC(0-t), AUC (0- ∞), Cp(10), Cp(20), Cp(30) , t1/2, Clearance (IV only), Volume of distribution (IV only), F (Inhaled Bioavailability) Lambda_z, Lambda_z_lower, Lambda_z_upper, #pts and r-squared as data permit	
Reporting of Partial Dose / No treatment		
If in a situation where a subject has received partial dose or a subject has received no treatment in a particular period, then they will be handled as given below:		
	Enrolled, Screened Population	Safety, PK Population
Listings, individual PK figures, Study Population tables without period treatment information	Include	Include
Summary PK figures, Safety and PK tables with treatment information	Include	Exclude
Graphical Displays		
Refer to IDSL Statistical Principals 7.01 to 7.13.		

CONFIDENTIAL

205920

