10.10.7. Safety Tables

Safety: Tables					
No.	Population	IDSL / Example Shell	Title	Programming Notes	Deliverable [Priority]
Adverse Events (AEs)					
3.1.	Safety	AE1CP	Summary of All Adverse Events by System Organ Class and Preferred Term	By Cohort	DR [1], SAC
3.2.	Safety	AE1CP	Summary of Drug-Related Adverse Events	By Cohort	DR [1], SAC
3.3.	Safety	AE1CP	Summary of Non-Serious Adverse Events	By Cohort	DR [1], SAC
3.4.	Safety	AE15	Summary of Common (>1 Subject) Non-serious Adverse Events by System Organ Class and Preferred Term (Number of Subjects and Occurrences)	By Cohort FDA, EudraCT	DR [1], SAC
Serious and Other Significant Adverse Events					
3.5.	Safety	AE16	Summary of Serious Adverse Events by System Organ Class and Preferred Term (Number of Subjects and Occurrences)	By Cohort FDA, EudraCT	DR [1], SAC
3.6.	Safety	AE1CP	Summary of Adverse Events Leading to Permanent Discontinuation of Study Drug or Withdrawal from Study	By Cohort	DR [1], SAC
Laboratory: Chemistry					
3.7.	Safety	LB1	Summary of Chemistry Laboratory Values	By Cohort	DR [1], SAC
3.8.	Safety	LB1	Summary of Change from Baseline for Chemistry Laboratory Values	By Cohort	DR [1], SAC

CONFIDENTIAL

205920

Safety: Tables					
No.	Population	IDSL / Example Shell	Title	Programming Notes	Deliverable [Priority]
Laboratory: Hematology					
3.9.	Safety	LB1	Summary of Haematology Laboratory Values	By Cohort	DR [1], SAC
3.10.	Safety	LB1	Summary of Change from Baseline for Haematology Laboratory Values	By Cohort	DR [1], SAC
Spirometry					
3.11.	Safety	LB1	Summary of Spirometry data	By Cohort.	DR [1], SAC
ECG					
3.12.	Safety	EG1	Summary of ECG Findings	By Cohort	DR [1], SAC
3.13.	Safety	EG2	Summary of ECG Values	By Cohort	DR [1], SAC
Vital Signs					
3.14.	Safety	VS1	Summary of Vital Signs	By Cohort	DR [1], SAC
3.15.	Safety	VS1	Summary of Change from Baseline for Vital Signs	By Cohort	DR [1], SAC
3.16.	Safety	VS7	Summary of Vital Sign Results Relative to Potential Clinical Importance (PCI) Criteria Post-Baseline Relative to Baseline	By Cohort	DR [1], SAC

CONFIDENTIAL

205920

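### The Group 2 reporting rule removes partially dosed, and therefore exposed, subject-periods from the safety tables by treatment, together with any adverse event that cut the dose short

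*SAP*

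**What the plan says.** The SAP contains two RAPs, one per group; this point concerns Group 2. Its Section 10.5.2 opens the rule with "If in a situation where a subject has received partial dose or a subject has received no treatment in a particular period" and then gives two rows of displays against two pairs of populations.

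- "Listings, individual PK figures, Study Population tables without period treatment information": such subjects are included for all populations.
- "Summary PK figures, Safety and PK tables with treatment information": they are included for the Enrolled and Screened populations and excluded for the Safety and PK populations.

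Section 4 defines the Safety population as follows: "Comprise of subjects who receive at least one dose of study medication. This population will be used for the study population and safety displays". A note adds that it is based on treatment actually received. Section 4.1 says: "The study endpoints will be reported using the populations detailed in Section 4 of this document regardless of whether the participants deviate from the protocol".

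The first-listed primary objective of Group 2 in Section 2.2 is "To evaluate the safety and tolerability of IH and IV Oxytocin".

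**The concern.** The two situations differ in the one respect that matters for safety. A participant who received nothing in a session was not exposed and has no place in that session's treatment column. A participant who received part of a dose was exposed, and the dose may be incomplete because of what that exposure did. Where that is so, exclusion depends on the outcome being summarised.

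At stake are the by-treatment summaries of adverse events, vital signs, ECG, laboratory values and spirometry that serve a primary objective. Table 3.6, "Summary of Adverse Events Leading to Permanent Discontinuation of Study Drug or Withdrawal from Study", is the most exposed: in a single-dose session, an event that stops administration leaves a partial dose behind, and the rule removes that subject-period from the table.

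**Working it through.** The plan gives no figure to reproduce. The check sets its sections side by side and then uses simple arithmetic on assumed numbers.

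**1. Are safety tables really covered?** Yes. The second row of the rule names them. The inclusion granted to the Enrolled and Screened populations gives no relief, because all 16 Group 2 safety tables (3.1 to 3.16, Section 10.10.7) are assigned to the Safety population.

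**2. Do those tables carry treatment information?** Very probably. The standard shells are not shown, and the programming notes in 10.10.7 organise the tables by cohort only. However, Section 5.1 requires displays of statistics to separate IV bolus from IV infusion, and 10.5.2 reports data by actual treatment. This step is an inference.

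**3. Does another section rescue these data?** No.
- Section 4 sets no full-dose condition and designates the Safety population for the safety displays.
- Section 4.1 keeps subjects in the Section 4 populations whatever their deviations.
- Section 10.7.1 puts available data from withdrawn participants into summary tables, but yields where something else is specified, and 10.5.2 specifies something else.
- The corresponding rule in the Group 1 RAP (10.5.2) deals with no treatment only and has no partial-dose exclusion.

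**4. Which period does an interrupting event fall in?** Section 10.4.2 assigns an event occurring after Period 1 dosing and before Period 2 dosing to Period 1, and one after Period 2 dosing to Period 2. An event that accompanies an incomplete dose therefore belongs to the period being excluded. Limiting the rule to one period does not save it.

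**5. Size and direction.** Let n be the number dosed on a treatment and x the number with the event. Let m be the number partially dosed and y the number of those m with the event.

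- With everyone exposed: x/n.
- As tabulated under the rule: (x − y)/(n − m).
- The rule understates incidence when (x − y)/(n − m) < x/n. Multiplying out gives mx < ny, that is, y/m > x/n: events are more frequent among the partially dosed than overall.

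The RAP states no Group 2 sample size, so n is assumed and varied.

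| Case | n | All exposed | Under the rule |
|---|---|---|---|
| Only event stopped the dose (x = y = m = 1) | 5 | 1/5 = 20% | 0/4 = 0% |
| Same | 10 | 1/10 = 10% | 0/9 = 0% |
| Same | 20 | 1/20 = 5% | 0/19 = 0% |
| Partial dose without an event; one event in a fully dosed participant (x = 1, y = 0, m = 1) | 10 | 1/10 = 10% | 1/9 = 11.1% |

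The first three rows show the informative case. The last shows the opposite direction.

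**The case against.** The rule itself is hard to defend for exposed participants, but several stronger readings are tempting and the document does not support them.

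- **That the event vanishes from the report.** It does not. The first row of the rule keeps listings, so withdrawal reasons (Listing 2), exposure (10), all adverse events (11), serious events (13) and events leading to withdrawal (14) still show the participant. What is lost is incidence by treatment, which listings do not supply.
- **That the participant leaves both treatment columns.** The reference to a particular period, in a two-session crossover, most naturally limits the exclusion to the affected session.
- **That the bias is always favourable.** The rule does not restrict partial dosing to cases caused by an adverse event. A dose left incomplete for another reason removes only a denominator count, as the last row of the table shows.
- **That Table 3.6 loses its content.** It also covers withdrawal from the study. A participant fully dosed in Session 1 who has an event and does not proceed to Session 2 is not a partial-dose case, and that event stays on the period-limited reading. Only events accompanying an incomplete dose drop out.
- **That 10.5.2 contradicts its own rule on actual treatment.** That rule allows stated exceptions, as does the general choice of the Safety population in Section 7. The conflict is with Sections 4 and 4.1.

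Two further points have some force. "Comprise of subjects who receive at least one dose of study medication" does not say whether part of a dose counts as a dose. But if it did not, a participant with only a partial dose would be outside the Safety population altogether, and the rule's first row, which includes such subjects in that population's listings, would make little sense. Second, the document does not say that any partial dose occurred, so the effect is contingent. That bears on severity. It does not justify the rule.

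**Conclusion.** The point holds in a limited form. Followed as written, the Group 2 rule takes exposed subject-periods out of the by-treatment safety summaries, against the Safety population definition and the rule on deviations, and unlike the Group 1 RAP. Where an adverse event caused the incomplete dose, the exclusion is informative and understates incidence for a primary objective: 1/10 becomes 0/9 with an assumed 10 dosed. Where the cause was something else, the distortion is a smaller denominator and may go the other way.

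This rests on three assumptions: that the safety tables have treatment columns, that a partial dose counts as exposure for the Safety population, and that at least one partial dose occurs. Because the events stay in the listings, probably only one period is affected and the occurrence is hypothetical, this is a correction that should be made. It is not a fault that invalidates the safety reporting.

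**What to change.** Split the rule in Section 10.5.2 of the Group 2 RAP.

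- **No treatment in a period:** exclude from that period's treatment columns, and say that the other period is unaffected.
- **Partial dose in a period:** keep the subject-period in all safety tables, including Table 3.6, under the treatment actually received, with a footnote identifying it as a partial dose. Limit the partial-dose exclusion to summary PK figures and PK tables.

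One added sentence in Section 4 should state that any amount of study medication counts towards the Safety population.

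The cost is a few lines of RAP text, one flag in the safety programs and a footnote. No data collection changes, and nothing here bears on how doses are given or stopped.

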10.5.3. Reporting Standards for Pharmacokinetic

Pharmacokinetic Concentration Data	
PC Windows Non-Linear (WNL) File	PC WNL file (CSV format) for the non compartmental analysis by Clinical Pharmacology Modelling and Simulation function will be created according to IDSL Standards. Note: Concentration values will be imputed as per GUI_51487
Descriptive Summary Statistics, Graphical Displays and Listings	Refer to IDSL PK Display Standards. Refer to IDSL Statistical Principle 6.06.1. Note: Concentration values will be imputed as per GUI_51487 for descriptive summary statistics/analysis and summarized graphical displays only.
NONMEM/Pop PK File	Pop-PK file (CSV format) for the POP-PK analysis by Clinical Pharmacology Modelling and Simulation function will be created according to the data specification detailed in Section 9.1 Data Specification of the Pop-PK RAP (RAP-IVF116828-201558-205920-PopPK, located in Cabinets/Study File/GR121619/_Project/Meta Analysis/ RAP-IVF116828-201558-205920-PopPK)
Pharmacokinetic Parameter Derivation	
PK Parameter to be Derived by Programmer	The following PK parameters will be derived by the Programmer: Cp10, Cp20 and Cp30 and pre-dose
Pharmacokinetic Parameter Data	
Is NQ impacted PK Parameters Rule Being Followed	Yes, refer to Standards for Handling NQ Impacted PK Parameters
Descriptive Summary Statistics, Graphical Displays and Listings	Refer to IDSL PK Display Standards. Refer to Standards for the Transfer and Reporting of PK Data using HARP

CONFIDENTIAL

205920

10.6. Appendix 6: Derived and Transformed Data

10.6.1. General

Multiple Measurements at One Analysis Time Point

 • Mean of the measurements will be calculated and used in any derivation of summary statistics but if listed, all data will be presented. • Participants having both High and Low values for Normal Ranges at any post-baseline visit for safety parameters will be counted in both the High and Low categories of “Any visit post-baseline” row of related summary tables. This will also be applicable to relevant Potential Clinical Importance summary tables.
Study Day

 • Calculated as the number of days from First Dose Date: 
 • Ref Date = Missing → Study Day = Missing • Ref Date < First Dose Date → Study Day = Ref Date – First Dose Date • Ref Date ≥ First Dose Date → Study Day = Ref Date – (First Dose Date) + 1

10.6.2. Study Population

Demographics
Age

 • GSK standard IDSL algorithms will be used for calculating age. • Randomization date will be used as reference date to calculate age
Body Mass Index (BMI)

 • Calculated as Weight (kg) / [Height (m)]²
Extent of Exposure

 • Number of days of exposure to study drug will be calculated based on the formula: Duration of Exposure in Days = Treatment Stop Date – (Treatment Start Date) + 1 • Participants who were randomized but did not report a treatment start date will be categorised as having zero days of exposure. • The cumulative dose will be based on the formula: Cumulative Dose = Sum of (Number of Days x Total Daily Dose) • If there are any treatment breaks during the study, exposure data will be adjusted accordingly.

10.6.3 Safety

ECG Parameters
RR Interval

 IF RR interval (msec) is not provided directly, then RR can be derived as : 
 [1] If QTcB is machine read & QTcF is not provided, then : $RR = [(QT/QTcB)^2] * 1000$ [2] If QTcF is machine read and QTcB is not provided, then: $RR = [(QT/QTcF)^3] * 1000$ If ECGs are manually read, the RR value preceding the measurement QT interval should be collected values THEN do not derive.
Corrected QT Intervals

 When not entered directly in the eCRF, corrected QT intervals using Bazett's (QTcB) and Fredericia's (QTcF) formulas will be calculated, in msec, depending on the availability of other measurements. IF RR interval (msec) is provided or calculated then missing QTcB and/or QTcF will be derived as : $QTcB = \frac{QT}{\sqrt{\frac{RR}{1000}}}$ $QTcF = \frac{QT}{\sqrt[3]{\frac{RR}{1000}}}$

CONFIDENTIAL

205920

10.7. Appendix 7: Reporting Standards for Missing Data

10.7.1. Premature Withdrawals

Element	Reporting Detail
General	
 • Subject study completion (i.e. as specified in the protocol) was defined as who has completed all phases of the study including the follow-up visit(s). • Withdrawn subjects may be replaced in the study. • All available data from participants who were withdrawn from the study will be listed and all available planned data will be included in summary tables and figures, unless otherwise specified.

10.7.2. Handling of Missing Data

Element	Reporting Detail
General	
 • Missing data occurs when any requested data is not provided, leading to blank fields on the collection instrument: 
 ○ These data will be indicated by the use of a "blank" in subject listing displays. Unless all data for a specific visit are missing in which case the data is excluded from the table. ○ Answers such as "Not applicable" and "Not evaluable" are not considered to be missing data and should be displayed as such.
Outliers	
 • Any participants excluded from the summaries and/or statistical analyses will be documented along with the reason for exclusion in the clinical study report.

10.7.2.1. Handling of Missing and Partial Dates

Element	Reporting Detail
General	
 • Partial dates will be displayed as captured in subject listing displays.
Adverse Events	
 • The eCRF does not allow for the possibility of partial dates. The eCRF and the site need to enter the full date or if not known, they would be required to complete an item level comment bubble to specify why the date is unknown. This would also be documented in the Data Quality Release Report by DM. • Completely missing start or end dates will remain missing, with no imputation applied. Consequently, time to onset and duration of such events will be missing
Concomitant Medications/Medical History	
 • Partial dates for any concomitant medications recorded in the CRF will be imputed using the following convention: 
 ○ If the partial date is a start date, a '01' will be used for the day and 'Jan' will be used for the month ○ If the partial date is a stop date, a '28/29/30/31' will be used for the day (dependent on the month and year) and 'Dec' will be used for the month. • The recorded partial date will be displayed in listings.

CONFIDENTIAL

205920

10.8. Appendix 8: Values of Potential Clinical Importance**10.8.1. Laboratory Values**

Haematology				
Laboratory Parameter	Units	Category	Clinical Concern Range	
			Low Flag (< x)	High Flag (>x)
Hematocrit	Ratio of 1	Male		0.54
		Female		0.54
		Δ from BL	↓0.075	
Haemoglobin	g/L	Male		180
		Female		180
		Δ from BL	↓25	
Lymphocytes	x10 ⁹ /L		0.8	
Neutrophil Count	x10 ⁹ /L		1.5	
Platelet Count	x10 ⁹ /L		100	550
While Blood Cell Count (WBC)	x10 ⁹ /L		3	20

Clinical Chemistry				
Laboratory Parameter	Units	Category	Clinical Concern Range	
			Low Flag (< x)	High Flag (>x)
Albumin	g/L		30	
Calcium	mmol/L		2	2.75
Creatinine	umol/L	Δ from BL		↑ 44.2
Glucose	mmol/L		3	9
Magnesium	mmol/L		0.5	1.23
Phosphorus	mmol/L		0.80	1.60
Potassium	mmol/L		3	5.5
Sodium	mmol/L		130	150
Total CO2	mmol/L		18.0	32.0

Liver Function				
Test Analyte	Units	Category	Clinical Concern Range	
ALT/SGPT	U/L	High	≥ 2x ULN	
AST/SGOT	U/L	High	≥ 2x ULN	
AlkPhos	U/L	High	≥ 2x ULN	
T Bilirubin	μmol/L	High	≥ 1.5xULN	
T. Bilirubin + ALT	μmol/L U/L	High	1.5xULN T. Bilirubin + ≥ 2x ULN ALT	

CONFIDENTIAL

205920

